## 5 Study Procedures

This is a tandem design trial comparing the diagnostic yield of HD-WLE and NBI with and without the use of an Olympus Disposable Distal Attachment cap.

### 5.1 Recruitment

Adult patients scheduled to undergo esophagogastroduodenoscopy (EGD) will be screened for the study. Patients will be identified as candidates for the study from the BJH Surgery Schedule the day before they come in. If they present for the evaluation and/or treatment of dysplastic lesions in BE, one of the investigators or a research assistant will discuss the study with potential participants in the pre-endoscopy area. Those subjects who qualify for the study based on inclusion/ exclusion criteria will be invited to participate. The consent process will take place in the pre-endoscopy area. Those patients who wish to participate will sign the informed consent document and proceed to EGD; randomization will take place after the patient is consented and before the procedure starts.

### 5.2 Intervention

After randomization, the endoscopist will then perform exam with or without cap using HD-WLE and NBI and identify visible lesions. Identified lesions will be recorded on the case report form using a blank clock face divided in four quadrants and with distance from the incisors in cm. The endoscope will then be withdrawn. A second endoscopist will then perform a second EGD with a cap if none was used on initial exam or without a cap if one was used on initial exam. The second endoscopist will be blinded to the results of the initial exam. If there is no physician available to perform second endoscopy then the patient will not be considered for the study. Visible lesions will be recorded in same format as initial exam. Finally, the endoscopist of record will biopsy or perform EMR of all noted lesions, which will be sent for pathological review, the results of which will be captured from the medical record. All procedures will be performed by a gastroenterologist experienced in EET or by a fellow under direct supervision. Patients will be contacted in 48 hours by phone by clinical staff to monitor for AEs

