#### **4.4 Randomization**

Consenting and eligible participants will be randomized to one of two arms. Participants in the first arm will undergo EGD with cap first, followed by EGD without cap. Participants in the second arm will undergo EGD without cap first, followed by EGD with cap. All participants will have EGD with and without cap; the randomization affects the order in which the procedures take place. The order of cap placement will be determined by a preprinted randomization sequence kept in an opaque envelope that will be opened after enrollment.

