### **9.2 Analysis methods**

This study will collect both categorical and quantitative demographic variables and endoscopy procedural details: procedure duration, diagnostic findings, and procedure complications. Pathology results will be recorded and the electronic medical record will be reviewed to extract any relevant clinical information. All complications will be noted. All information will be transferred into a database. The categorical variables will be summarized using frequencies and percents, while the quantitative variables will be summarized using means and standard deviations. Chi square test will be used for categorical variables while student's t test will be used for quantitative variables to test the difference between the study groups. Additionally, multivariable analysis will be used in order to identify factors associated with success increasing diagnostic yield. Continuous variables with a non-normal distribution will be compared using the Wilcoxon rank-sum test. The statistical software program SPSS will be used for analysis. A two sided p value of < 0.05 will be considered significant.

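### No step settles who does which exam before the cap order is revealed, so operator skill could follow cap status

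*Combined protocol and SAP*

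**What the plan says.** Section 5.2 (Intervention) describes two exams of the same patient by two people: "A second endoscopist will then perform a second EGD with a cap if none was used on initial exam", and the reverse if the first exam used the cap. The second operator is blinded to the first exam's findings. On qualifications the section says "All procedures will be performed by a gastroenterologist experienced in EET or by a fellow under direct supervision". On availability it says "If there is no physician available to perform second endoscopy then the patient will not be considered for the study". It refers to an endoscopist, a second endoscopist and an endoscopist of record, but does not link experience level to either exam.

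Section 4.4 (Randomization) has every patient examined both ways: "the randomization affects the order in which the procedures take place". The order comes from a "preprinted randomization sequence kept in an opaque envelope that will be opened after enrollment". Section 5.1 adds that "randomization will take place after the patient is consented and before the procedure starts". Neither section has a step that assigns operators.

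The primary endpoint (section 2.1) is the share of exams in which a lesion was seen and then proven dysplastic or malignant on pathology. Section 9.1 assumes a 15% gain with the cap and 170 patients.

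Section 9.2 states "Chi square test will be used for categorical variables". It also says "multivariable analysis will be used in order to identify factors associated with success increasing diagnostic yield", without naming covariates. It lists duration, findings and complications as procedural details, and plans a review of the medical record for relevant clinical information.

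**The concern.** The endpoint depends on what the operator sees, so it depends on operator skill. Because the two exams have different operators, each within-patient difference mixes the effect of the cap with the difference between two people, who may be unequally experienced.

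Randomising the order separates the two only if operator roles do not depend on that order. Keeping the envelope closed until enrollment protects patient selection. It does not protect the choice of operator after opening. If that choice were made with the order known, the more experienced operator could more often have the cap exam, or more often the other one. The estimated cap effect would then be biased in the corresponding direction.

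**Working it through.** **The plan's own figure.** The 170 patients cannot be reproduced uniquely, because section 9.1 gives neither baseline yield nor discordance. For an absolute 15-point gain:
- The unpaired formula gives about 170 per arm at baselines of about 34-54%, and about 170 in total (172) near a 78% baseline.
- A McNemar formula gives 166-173 patients at discordance 0.48-0.50.

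This point does not rest on how 170 was derived.

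**Bias formula.** Let m be the share of patients whose two operators are one experienced gastroenterologist and one fellow. Let s be the share of those patients in whom the fellow does the no-cap exam, and g the difference in yield between the two levels. The documents give none of the three; all are assumptions. A mixed pair adds +g with probability s and -g with probability 1-s, so

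bias = m[s·g - (1-s)·g] = m(2s-1)g.

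- Roles set independently of order, with the two orders equally likely: s = 0.5, so bias = 0.
- Illustration, m = 0.5, s = 0.75, g = 0.10: 0.5 × 0.5 × 0.10 = 0.025, or 2.5 points. That is 2.5/15 = one sixth of the assumed gain, read as absolute.
- Mirror case, s = 0.25: -2.5 points.
- Wider inputs, m 25-100%, s 60-90%, g 5-10 points: from 0.25 × 0.2 × 0.05 = 0.25 points to 1 × 0.8 × 0.10 = 8 points. Letting s run from 10% to 90% makes this -8 to +8 points, passing through zero. It is also zero if supervision removes the skill gap (g = 0).

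For scale, the paired standard error, √(D/170), is 3.4, 4.2 and 4.9 points at discordance D = 0.2, 0.3 and 0.4. The illustrative bias is smaller than one standard error.

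**Separate check: the unpaired test.** With yield p on both exams and no cap effect, the chi-square uses variance 2p(1-p)/170, while the true variance of the difference is D/170. At p = 0.5 and D = 0.3 the ratio of standard errors is √(0.5/0.3) = 1.29. The effective critical value is 1.96 × 1.29 = 2.53, and the two-sided error is about 1.1%. Simulation (400,000 sets of 170 pairs, no bias) gives:

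| No-cap yield | D = 0.4 | D = 0.3 | D = 0.2 |
|---|---|---|---|
| 50% | 2.6% | 1.0% | 0.2% |
| 35% | 3.6% | 1.6% | 0.3% |
| 20% | 8.1% | 4.4% | 1.4% |

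The test is conservative whenever D < 2p(1-p), that is, when the two exams are positively correlated. The 8.1% cell has D = 0.4 > 2 × 0.2 × 0.8 = 0.32, so it needs a negative correlation, which is hard to credit for two exams of one oesophagus. This defect would exist even with perfect operator allocation.

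**Adjusting for recorded level.** In a simulated GEE with no true cap effect and the illustrative m, s and g, terms for cap, exam position and operator level moved the estimate from 2.5 to 0.0 points. Type I error was 4.4-4.9% and the standard error 4-7% larger. The 0.0 follows partly from the set-up, because skill was made to depend only on recorded level.

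**The case against.** The strongest reply is that the harm depends on conduct the documents do not describe. Section 5.2 can be read as setting roles by position, with one endoscopist first and a second one after. Section 5.1 finds candidates from the previous day's surgery schedule. On that reading the randomised order balances operator against cap. The second-physician requirement also means that two operators must be available before a patient is considered, which narrows the room for choice after the reveal. Direct supervision may shrink the skill gap. All of this stands as mitigation, but none of it says who takes which exam or that the roles cannot be swapped once the envelope is open.

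A reader might infer that the plan could neither detect nor correct such a bias. That is too strong. The case report form is not in the documents, section 9.2 includes a record review, and its multivariable analysis names no covariates, so operator is not excluded. Recording and adjustment are unspecified, not shown to be absent.

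A reader might also infer an inflated false-positive rate. With a 2.5-point bias McNemar would reject 8.2%, 9.0% and 11.2% of the time at D = 0.4, 0.3 and 0.2, but McNemar is not the planned test. The planned chi-square at 50% yield gives 4.7%, 2.5% and 0.8%, and it stays below 5% in six of the nine yield and discordance cells examined. The error rates do not carry the point; possible bias in the estimate does.

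Nor does the point extend to a supervisor passing on first-exam findings, since section 5.2 already blinds the second operator to them.

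**Conclusion.** The gap is real but conditional. Operator and cap status change together within every patient, operators may differ in experience, the order is known before the exams, and nothing fixes roles first. Expected bias is zero if roles are set independently of the order; otherwise it can go either way. The documents do not show that operators are matched to exams after the reveal, and they do not support any estimate of size. The 2.5 points is an illustration resting on three assumed inputs, within a range that includes zero. This is a cheap clarification worth making, not evidence that the comparison is biased.

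The unpaired chi-square is a separate weakness. It ignores within-patient correlation and is generally conservative when that correlation is positive.

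**What to change.** 1. **Sections 4.4 and 5.2.** Before the envelope is opened, name the first and second operators and record their level (experienced gastroenterologist or fellow) on the case report form. Log any later change as a deviation. If followed, this alone removes the expected bias. The cost is two form fields and the logging. No extra staff or patients are needed, because a second physician must already be available.

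2. **Section 9.2, as a separate point.** Replace the unpaired chi-square for the cap comparison with a paired analysis: McNemar, conditional logistic regression or GEE. This is a real change, because the section now contains no paired test.

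3. **Optional sensitivity analysis.** Add exam position and recorded operator level to the paired model. In the simulated scenario the standard error rises by about 4-7%, and power for a true 15-point gain (50% to 65%) is still about 95%. These terms do not correct skill differences between operators of the same level, so step 1 remains the main protection.

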## 6 REGULATORY AND REPORTING REQUIREMENTS

The entities providing oversight of safety and compliance with the protocol require reporting as outline below.

The Washington University Human Research Protection Office (HRPO) requires that all events meeting the definition of unanticipated problem or serious noncompliance be reported as outlined in Section 7.2.

### 6.1 Definitions

#### 6.1.1 Adverse Events (AEs)

**Definition:** any unfavorable medical occurrence in a human subject including any abnormal sign, symptom, or disease.

**Grading:** the descriptions and grading scales found in the revised NCI Common Terminology Criteria for Adverse Events (CTCAE) version 4.0 will be utilized for all toxicity reporting. A copy of the CTCAE version 4.0 can be downloaded from the CTEP website.

**Attribution (relatedness), Expectedness, and Seriousness:** the definitions for the terms listed that should be used are those provided by the Department of Health and

Human Services' Office for Human Research Protections (OHRP). A copy of this guidance can be found on OHRP's website: <http://www.hhs.gov/ohrp/policy/advevntguid.html>

Risks associated with this study include risk of breach of confidentiality and having to be under sedation for an additional 2-5 minutes while the second exam of the study is being performed.

#### **6.1.2 Serious Adverse Event (SAE)**

**Definition:** any adverse drug experience occurring at any dose that results in any of the following outcomes:

- Death
- A life-threatening adverse drug experience
- Inpatient hospitalization or prolongation of existing hospitalization
- A persistent or significant disability/incapacity (i.e., a substantial disruption of a person's ability to conduct normal life functions)
- A congenital anomaly/birth defect
- Any other experience which, based upon appropriate medical judgment, may jeopardize the subject and may require medical or surgical intervention to prevent one of the outcomes listed above

#### **6.1.3 Unexpected Adverse Experience**

**Definition:** any adverse drug experience, the specificity or severity of which is not consistent with the current investigator brochure (or risk information, if an IB is not required or available).

#### **6.1.4 Life-Threatening Adverse Experience**

**Definition:** any adverse drug experience that places the subject (in the view of the investigator) at immediate risk of death from the reaction as it occurred, i.e., it does not include a reaction that, had it occurred in a more severe form, might have caused death.

#### **6.1.5 Unanticipated Problems**

**Definition:**

- unexpected (in terms of nature, severity, or frequency) given (a) the research procedures that are described in the protocol-related documents, such as the IRB-approved research protocol and informed consent document; and (b) the characteristics of the subject population being studied;
- related or possibly related to participation in the research ("possibly related" means there is a reasonable possibility that the incident, experience, or outcome may have been caused by the procedures involved in the research); and
- suggests that the research places subjects or others at a greater risk of harm (including physical, psychological, economic, or social harm) than was previously known or recognized.

#### **6.1.6 Noncompliance**

**Definition:** failure to follow any applicable regulation or institutional policies that govern human subjects research or failure to follow the determinations of the IRB. Noncompliance may occur due to lack of knowledge or due to deliberate choice to ignore regulations, institutional policies, or determinations of the IRB.

### 6.1.7 Serious Noncompliance

**Definition:** noncompliance that materially increases risks, that results in substantial harm to subjects or others, or that materially compromises the rights or welfare of participants.

### 6.1.8 Protocol Exceptions

**Definition:** A planned deviation from the approved protocol that are under the research team's control. Exceptions apply only to a single participant or a singular situation.

Local IRB pre-approval of all protocol exceptions must be obtained prior to the event. For secondary sites, the Washington University PI will issue approval of the exception, but it must also be submitted to the local IRB with documentation of approval forwarded to Washington University. Washington University IRB approval is not required for protocol exceptions occurring at secondary sites.

## 6.2 Reporting to the Human Research Protection Office (HRPO) at Washington University

The PI is required to promptly notify the IRB of the following events:

- Any unanticipated problems involving risks to participants or others which occur at WU, any BJH or SLCH institution, or that impacts participants or the conduct of the study.
- Noncompliance with federal regulations or the requirements or determinations of the IRB.
- Receipt of new information that may impact the willingness of participants to participate or continue participation in the research study.

These events must be reported to the IRB within **10 working days** of the occurrence of the event or notification to the PI of the event. The death of a research participant that qualifies as a reportable event should be reported within **1 working day** of the occurrence of the event or notification to the PI of the event.

## 6.3 Reporting to the Quality Assurance and Safety Monitoring Committee (QASMC) at Washington University

The PI is required to notify the QASMC of any unanticipated problem occurring at WU or any BJH or SLCH institution that has been reported to and acknowledged by HRPO as reportable. (Unanticipated problems reported to HRPO and withdrawn during the review process need not be reported to QASMC.)

QASMC must be notified within **10 days** of receipt of IRB acknowledgment via email to a QASMC auditor.

## 6.4 Reporting Requirements for Secondary Sites

The research team at each secondary site is required to promptly notify the Washington University PI and research coordinator of all reportable events (as described in Section 6.6) within **1 working day** of the occurrence of the event or notification of the secondary site's PI of the event. This notification may take place via email if there is not yet enough information for a formal written report (using either an FDA MedWatch form if required or an institutional SAE reporting form if not). A formal written report must be sent to the Washington University PI and research coordinator within **10 working days** of the occurrence of the event or notification of the secondary site's PI of the event. The death of a research participant that qualifies as a reportable event should be reported within **1 working day** of the occurrence of the event or notification of the secondary site's PI of the event.

The research team at a secondary site is responsible for following its site's guidelines for reporting applicable events to its site's IRB according to its own institutional guidelines.

### **6.5 Reporting to Secondary Sites**

The Washington University PI (or designee) will notify the research team at each secondary site of all reportable events that have occurred at other sites within **10 working days** of the occurrence of the event or notification of the PI of the event. This includes events that take place both at Washington University and at other secondary sites, if applicable.

### **6.6 Timeframe for Reporting Required Events**

Adverse events will be tracked for 48 hours after EGD.

## **7 Data and Safety Monitoring Plan**

In compliance with the Washington University Institutional Data and Safety Monitoring Plan, an independent Data and Safety Monitoring Committee (DSMC) will be specifically convened for this trial to review toxicity data at least every 6 months following the activation of the first secondary site. A DSMC will consist of no fewer than 3 members including 2 clinical investigators and a biostatistician. Like investigators, DSMC members are subject to the Washington University School of Medicine policies regarding standards of conduct. Individuals invited to serve on the DSMC will disclose any potential conflicts of interest to the trial principal investigator and/or appropriate university officials, in accordance with institution policies. Potential conflicts that develop during a trial or a member's tenure on a DSMC must also be disclosed.

The DSM report will be prepared by the study statistician with assistance from the study team, will be reviewed by the DSMC, and will be submitted to the Quality Assurance and Safety Monitoring Committee (QASMC). This report will include:

- HRPO protocol number, protocol title, Principal Investigator name, data coordinator name, regulatory coordinator name, and statistician
- Date of initial HRPO approval, date of most recent consent HRPO approval/revision, date of HRPO expiration, date of most recent QA audit, study status, and phase of study
- History of study including summary of substantive amendments; summary of accrual suspensions including start/stop dates and reason; and summary of protocol exceptions, error, or breach of confidentiality including start/stop dates and reason
- Study-wide target accrual and study-wide actual accrual including numbers from participating sites
- Protocol activation date at each participating site
- Average rate of accrual observed in year 1, year 2, and subsequent years at each participating site
- Expected accrual end date, accrual by site, and accrual by cohort
- Objectives of protocol with supporting data and list the number of participants who have met each objective
- Measures of efficacy
- Early stopping rules with supporting data and list the number of participants who have met the early stopping rules
- Summary of toxicities at all participating sites and separated by cohorts
- Abstract submissions/publications
- Summary of any recent literature that may affect the safety or ethics of the study

Further DSMC responsibilities are described in the DSMC charter.

Until such a time as the first secondary site activates this protocol, a semi-annual DSM report to be prepared by the study team will be submitted to the QASM Committee beginning 6 months after study activation at Washington University.

The study principal investigator and coordinator will monitor for serious toxicities on an ongoing basis. Once the principal investigator or coordinator becomes aware of an adverse event, the AE will be reported to the HRPO and QASMC according to institutional guidelines (please refer to Section 7.0).

Refer to the Washington University Quality Assurance and Data Safety Monitoring Committee Policies and Procedures for full details on the responsibilities of the DSMC at <https://siteman.wustl.edu/wp-content/uploads/2015/10/QASMC-Policies-and-Procedures-03.31.2015.pdf>

## **8 AUDITING**

As coordinating center of this trial, Washington University (via the Quality Assurance and Safety Monitoring Committee (QASMC)) will monitor each participating site to ensure that all protocol requirements are being met; that applicable federal regulations are being followed; and that best practices for patient safety and data collection are being followed per protocol. Participating sites will be asked to send copies of all audit materials, including source documentation. The audit notification will be sent to the Washington University Research Patient Coordinator, who will obtain the audit materials from the participating institution.

Notification of an upcoming audit will be sent to the research team one month ahead of the audit. Once accrual numbers are confirmed, and approximately 30 days prior to the audit, a list of the cases selected for review (up to 10 for each site) will be sent to the research team. However, if during the audit the need arises to review cases not initially selected, the research team will be asked to provide the additional charts within two working days.

Items to be evaluated include:

- Subject screening and enrollment
- Reporting of adverse events
- Maintenance of HIPAA compliance
- Completeness of regulatory documentation
- Completeness of participant documentation
- Acquisition of informed consent
- IRB documentation
- Issues of protocol adherence

Additional details regarding the auditing policies and procedures can be found at <https://siteman.wustl.edu/wp-content/uploads/2015/10/QASMC-Policies-and-Procedures-03.31.2015.pdf>

